#### 18.1.2. Injection Site Reactions (Solicited Adverse Events)

Solicited AEs are a list of pre-defined events or symptoms that participants are assessed for at designated time points post dose. Injection site assessment will be performed by the investigator or designee at 1 hour, 4 hours, 24 hours post dose, and on Day 3, and Day 29 based on the following reactions:

Tenderness

- Pain
- Erythema/Redness
- Induration/Swelling
- Other reactions as observed by the investigator.

Each of these reactions, if observed, will be graded for severity on a 4-point categorical scale of Mild, Moderate, Severe, and Potentially Life-threatening, as per protocol. Solicited AEs will be tabulated for incidence of occurrence for number of participants by timepoint and treatment group. The summaries will be presented by the specific local injection site reaction and the severity of the assessment of the condition as recorded on the eCRF data. The summaries will also be presented by severity and overall for all timepoints, overall for all VIS954 treatment groups, and for all participants. The number of participants experiencing any injection site reactions will be plotted by treatment group and severity in a stacked bar graph.

### 18.1.3. TEAEs Leading to Withdrawal from the Study

TEAEs leading to withdrawal from the study will be identified in the AE listing by using the recorded response to the relevant question in the eCRF page.

#### 18.1.4. Serious Adverse Events

Serious adverse events (SAEs) are those events recorded as "Serious" on the Adverse Events page of the eCRF and will be listed separately in addition to being included in other AE listings.

#### 18.1.5. Immediately Reportable Events

Immediately Reportable Events (IREs) are those events recorded as "Immediately Reportable Event" on the Adverse Events page of the eCRF and will be listed separately in addition to being included in other AE listings.

#### 18.1.6. Deaths

If any participants die during the study as recorded in seriousness criteria of the SAE page of the eCRF,

Visterra Insert
Customer Name/ Logo
Protocol VIS954-101
Page 34 of 42

Statistical Analysis Plan

the information will be presented in a separate data listing in addition to being included in other AE listing.

## 18.2. Laboratory Evaluations

Results from the local laboratory will be included in the reporting of this study for clinical laboratory analytes in the Hematology, Serum Chemistry and Coagulation, and Urinalysis panels. A list of laboratory assessments to be included in the outputs is included in Appendix 2 of the clinical study protocol, Section 10.2. Presentations will use SI Units.

Quantitative laboratory measurements reported as "< X", i.e., BLQ, or "> X", i.e., above the upper limit of quantification (ULQ), will be converted to X for the purpose of quantitative summaries, but will be presented as recorded, i.e., as "< X" or "> X" in the listings.

The following summaries will be provided for laboratory data:

- Observed and change from baseline by treatment group and visit (for quantitative measurements).
- For participants with both baseline results as well as for the postbaseline visit, shift from baseline
  according to normal range criteria by treatment group and visit (for quantitative measurements and
  categorical measurements)

### 18.2.1. Laboratory Reference Ranges

Quantitative laboratory measurements will be compared with the relevant laboratory reference ranges in SI units and categorized as:

- Low: Below the lower limit of the laboratory reference range.
- Normal: Within the laboratory reference range (upper and lower limit included).
- High: Above the upper limit of the laboratory reference range.

## 18.2.2. Toxicity Grading for Laboratory Data

The standardized grading scales based on the FDA Guidance for Industry: Toxicity Grading Scale for Healthy Adult and Adolescent Volunteers Enrolled in Preventative Vaccine Clinical Trials, Sep 2007 are presented in clinical study protocol Section 10.5. Based on these criteria the clinically significant

laboratory test abnormalities assessed as AEs by the principal investigator will be presented in the AE listings.

#### 18.3. ECG Evaluations

Results from the central ECG (Electrocardiogram) Reading Centre will be included in the reporting of this study.

The following ECG parameters will be reported for this study:

- PR Interval (msec)
- QRS Interval (msec)
- QT Interval (msec)
- QTc Interval (msec)
- QTcF Interval (msec) [derived]
- Hear Rate (HR) (beats per minute [bpm])
- Overall assessment of ECG (Investigator's judgment):
  - Normal
  - Abnormal, Not Clinically Significant (ANCS)
  - Abnormal, Clinically Significant (ACS)

The following summaries will be provided for ECG data:

- Observed and change from baseline descriptive statistics by treatment group and visit (for quantitative measurements)
- Incidence of clinically significant Overall ECG assessments based on investigator's assessment by treatment group and visit.

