8.10 Health Economics or Medical Resource Utilization and Health Economics

Health economics or medical resource utilization and health economics parameters are not evaluated in this study.

Clinical Study Protocol VIS954-101

9 Statistical Considerations

The statistical analysis plan will be finalized prior to database lock and it will include a more technical and detailed description of the statistical analyses described in this section. This section is a summary of the planned statistical analyses of the most important endpoints including primary and key secondary endpoints.

In general, descriptive statistics for continuous variables will be summarized by treatment group using number of participants, arithmetic mean, standard deviation, median, minimum and maximum; descriptive statistics for categorical data will be summarized by treatment group using frequency counts and percentages. The placebo participants will be pooled into a single placebo group for summaries and presentations. Therefore, treatment group will refer to each of the dose level of VIS954 and pooled placebo.

Adverse events, clinical laboratory tests, vital sign measurements, ECGs, physical examinations, and injection site reactions are the primary endpoints of the study. All AEs will be coded by Medical Dictionary for Regulatory Activities (MedDRA) system organ class and preferred term.

The incidence of TEAEs will be summarized by treatment group.

Participants with clinically significant abnormalities in clinical laboratory tests, vital signs, physical examinations, and injection site reactions will be summarized by count and percentage.

In general, missing data will be left missing, analyses will be conducted based on the available cases and will be clearly reflected by reporting a category of "NOT REPORTED" or reflected in the total number of participants used for analysis.

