9.2.2.4 Electrocardiogram Data

Standard 12-lead ECG results will be listed for each participant. Descriptive statistics will be calculated for ECG parameters. The incidence of abnormalities, based on the clinical interpretations from the principal investigator, will be summarized.

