### 18.5. Physical Examination

Physical exam results will be listed including specification of any abnormalities observed and the investigators assessment of the abnormality. A shift table summarizing the changes in physical examination assessments from baseline to post baseline visits will be provided.

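### SAP 18.3 tabulates only clinically significant ECG assessments, while Protocol 9.2.2.4 plans the incidence of ECG abnormalities without that limit

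*SAP*

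**What the plan says.** Protocol section 9 makes ECG part of the primary assessment: "Adverse events, clinical laboratory tests, vital sign measurements, ECGs, physical examinations, and injection site reactions are the primary endpoints of the study". For ECG specifically, Protocol 9.2.2.4 states: "The incidence of abnormalities, based on the clinical interpretations from the principal investigator, will be summarized". It also provides a listing: "Standard 12-lead ECG results will be listed for each participant".

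Protocol section 9 has a separate rule for findings that count only when clinically significant: "Participants with clinically significant abnormalities in clinical laboratory tests, vital signs, physical examinations, and injection site reactions will be summarized by count and percentage". ECG is not named there.

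SAP 18.3 records the investigator's overall ECG judgement in three categories: Normal, ANCS and ACS. It then names two summaries. One gives descriptive statistics, observed and change from baseline, for the quantitative ECG measurements. The other is "Incidence of clinically significant Overall ECG assessments based on investigator's assessment by treatment group and visit". No summary of the ANCS category and no ECG shift table is named.

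**The concern.** The two documents count different participants as having an ECG abnormality. Someone with an ANCS tracing after dosing has an event under the protocol's summary and none under the SAP's. The SAP governs the programming, so following 18.3 as written would leave a summary of a primary endpoint narrower than the protocol describes, with no visible explanation.

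The omitted category is also the one that adds information. Under Protocol 10.3.1, an ECG abnormality that the investigator considers clinically significant meets the adverse event definition. ACS findings that arise after dosing should therefore already reach the adverse event tables. The ANCS count has no such second route. In a first-in-human study with small dose groups, a reader would want to see whether minor findings become more frequent as dose rises without assembling this from listings.

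**Working it through.** No sample-size or power figure bears on this point, so the check is mainly a comparison of texts.

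**1. What each text counts**

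| Overall ECG assessment | Protocol 9.2.2.4 | SAP 18.3 incidence summary |
|---|---|---|
| Normal | not an abnormality | not counted |
| ANCS | abnormality | not counted |
| ACS | abnormality | counted |

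The texts differ in the ANCS row only.

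**2. Is the protocol's wording likely to be deliberate?** Section 9 applies the clinical-significance filter to four named assessments, and ECG is not one of them. Vital signs are. SAP 18.4 applies the filter to vital signs, in line with the protocol; SAP 18.3 applies the same filter to ECG, where the protocol has none.

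**3. Does the SAP agree with itself?** SAP 6.1 sets a general rule that qualitative variables are shown with a percentage for every class, and the overall ECG assessment is a qualitative variable with three classes. SAP 6.6, in its rule on unscheduled measurements, mentions incidence tables of abnormal results without a significance limit. Both point to a wider table than the one 18.3 names.

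**4. Is the change declared?** The readable entry in SAP 3.3 concerns disposition only. A second bullet is redacted.

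**5. Where else would an ANCS finding show?** A finding that alters PR, QRS, QT, QTc, QTcF or heart rate contributes to the descriptive statistics in 18.3. A morphology or rhythm finding that leaves these unchanged would be in the listing only.

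**6. Size**

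Inputs from the documents: 6 cohorts of 9 give 6 × 9 = 54 participants, of whom 6 × 7 = 42 receive VIS954 and 6 × 2 = 12 receive placebo. The Schedule of Assessments marks one postdose ECG, on Day 2. One participant is 1/7 = 14.3 percentage points of a dose group and 1/12 = 8.3 of pooled placebo.

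The documents give no rate for ANCS or ACS findings. The rates p below are assumptions, used only to show how far the result depends on them. With one scheduled postdose tracing per participant, P(no event among n) = (1 − p)^n.

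| Assumed ACS rate on Day 2 | P(no event in 54) | P(no event in a group of 7) |
|---|---|---|
| 0.1% | 94.7% | 99.3% |
| 0.5% | 76.3% | 96.6% |
| 1% | 58.1% | 93.2% |
| 2% | 33.6% | 86.8% |
| 5% | 6.3% | 69.8% |

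P(no event in 54) falls to one half at p = 1 − 0.5^(1/54) = 1.28%.

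If any abnormality is counted (ANCS plus ACS), assumed rates of 5%, 10% and 20% give 54p = 2.7, 5.4 and 10.8 expected participants, and P(no event in 54) of 6.3%, 0.3% and below 0.1%. These rates are prevalences on Day 2. They include tracings already abnormal at baseline, so they do not measure new postdose changes.

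**The case against.** The strongest reply is that the SAP already covers this. SAP 6.1 calls for every class of a qualitative variable, 18.3 lists all three categories among the parameters to be reported, and SAP section 8 leaves table content to templates that are not available here. On that reading, the bullet in 18.3 merely singles out one row. This has some force: what the shells contain cannot be confirmed, and the redacted bullet in 3.3 might declare the change. But 18.3 is the specific section, and it names the summaries to be provided. If 6.1 is meant to prevail, 18.3 still needs correcting to say so.

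A second reply is that an abnormality based on the investigator's clinical interpretation could already include the judgement of significance, and that Protocol section 9 leaves technical detail to the SAP. That reading is possible. It is weakened because the protocol uses the term clinically significant where it wants that limit, and leaves ECG out there.

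Third, little may be lost. Interval and heart-rate changes are tabulated, ANCS tracings are listed, and SAP 6.7 plans no hypothesis tests. All of this stands. A reader might infer that a dose-related ECG effect would be visible only in listings; that goes too far, because an effect on intervals or rate would show in the descriptive tables. What remains is the group of ANCS findings not expressed in those measurements.

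Fourth, the missing shift table might be read as a further departure. It is not one. The SAP plans shifts from baseline for laboratory data and, for physical examination, "A shift table summarizing the changes in physical examination assessments from baseline to post baseline visits will be provided". Protocol 9.2.2.2 promises shift tables for selected laboratory parameters only, and no protocol text promises one for ECG.

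**Conclusion.** The point holds as a mismatch between protocol and SAP on how a primary safety endpoint is summarised, together with an inconsistency within the SAP between 18.3 and sections 6.1 and 6.6. It rests on the natural reading of Protocol 9.2.2.4 and on the visible text. A hidden entry in SAP 3.3 or a fuller table shell cannot be excluded.

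The practical effect is confined to ANCS findings that the interval and heart-rate summaries do not reflect. How many there would be is unknown.

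A reader might also infer that the clinically significant table will probably be empty. The documents do not support that as a statement of fact. It follows for the whole study only if the ACS rate is below about 1.3% per participant. That is plausible in volunteers found healthy on a screening ECG, but no document gives the rate, and at an assumed 2% the table is more likely than not to contain an event. An empty table would also be a legitimate safety result in its own right. The case for changing the SAP is the mismatch, which does not depend on any assumed rate.

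**What to change.** In SAP 18.3, replace the incidence bullet with the number and percentage of participants in each overall ECG category (Normal, ANCS, ACS) by treatment group and visit. The clinically significant count stays as one row, so nothing now planned is lost, and the section then agrees with Protocol 9.2.2.4 and SAP 6.1. If the narrower count is intended, the alternative is to declare it with a reason in SAP 3.3.

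A baseline-to-Day 2 shift table of the three categories, in line with those planned for laboratory and physical examination data, is an optional low-cost addition; it corrects no protocol departure.

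The main change costs one SAP sentence and one table shell, using data already collected. Protocol section 9 has the SAP finalised before database lock. The change belongs before lock and unblinding, so that the choice of table cannot appear to depend on the results.

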## 18.4. Vital Signs

The following Vital Signs measurements will be reported for this study:

- Systolic Blood Pressure (mmHg)
- Diastolic Blood Pressure (mmHg)

- Pulse Rate (bpm)
- Respiratory Rate (breaths/min)
- Temperature (°C)
- Height (cms)
- Weight (kg)
- BMI (kg/m²)

The following summaries will be provided for vital signs data:

- Observed and change from baseline descriptive statistics by treatment group, visit, and timepoint.
- Incidence of clinically significant vital signs assessment based on investigator's assessment by treatment group, visit, and timepoint.

### 18.5. Physical Examination

Physical exam results will be listed including specification of any abnormalities observed and the investigators assessment of the abnormality. A shift table summarizing the changes in physical examination assessments from baseline to post baseline visits will be provided.

# 18.6. Wong-Baker FACES Pain Rating Scale

Participants will assess the pain associated with the injection using a validated pain scale, the Wong-Baker FACES Pain Rating Scale at the same time points when solicited AEs will be assessed. Data for the Wong-Baker FACES Pain Rating Scale scores for pain perception will be summarized using descriptive statistics.

# 19. DATA NOT SUMMARIZED OR PRESENTED

The other variables and/or domains not summarized or presented are:

Comments

These domains and/or variables will not be summarized or presented, but will be available in the clinical study database, SDTM and/or ADaM datasets.

Page 37 of 42

# APPENDIX 1. PROGRAMMING CONVENTIONS FOR OUTPUTS

# **IQVIA Output Conventions**

Outputs will be presented according to the following:

#### Dates & Times

Depending on data available, dates and times will take the form yyyy-mm-ddThh:mm:ss.

# **Spelling Format**

English US

# Presentation of Treatment Groups

For outputs, treatment groups will be represented as follows and in the given order:

Treatment Group	For Tables and Listings	For Figures
Placebo (where applicable)	Placebo (where applicable)	Placebo (where applicable)
CCI VIS954	VIS954	CCI
CCI VIS954	CCI VIS954	
CCI VIS954	CCI VIS954	
CCI VIS954	CCI VIS954	

Page 38 of 42

Statistical Analysis Plan

		T
Treatment Group	For Tables and Listings	For Figures
Placebo	Placebo	Placebo
Tiaccoo	Taccoo	Taccoo
(where applicable)	(where applicable)	(where applicable)
VIS954	VIS954	CCI
VIS954	VIS954	
All VIS954 Treated	VIS954	VIS954
(where applicable)	(where analicable)	(where emplicable)
(where applicable)	(where applicable)	(where applicable)
A11 Cubiacts	All Subjects	All Subjects
All Subjects All Subjects		All Subjects
(where applicable)	(where applicable)	(where applicable)
, , ,	, , ,	,

## Presentation of Visits

Include rows/columns as appropriate.

For outputs, visits will be represented as follows and in that order:

Long Name (default)	Short Name
Screening, Day -28	Scr (V1)
Baseline, Day -1	BL (V2)
Day 1	D1 (V3)
Day 2	D2 (V4)
Day 57	D57 (V14)
EOS Day 71/ET	D71 (V15)

Page 39 of 42

Statistical Analysis Plan

# Listings

[figure not shown]
All listings will be ordered by the following (unless otherwise indicated in the template):

- Treatment group
- Participant ID
- Date and time (where applicable).

# APPENDIX 2. PARTIAL DATE CONVENTIONS

# **Algorithm for Treatment Emergence of Adverse Events:**

START DATE	STOP DATE	ACTION
Known	Known/Partial/ Missing	If start date < study med start date, then not TEAE  If start date >= study med start date, then TEAE
Partial, but known components show that it cannot be on or after study med start date	Known/Partial/ Missing	Not TEAE
Partial, could be on or after study med start date OR Missing	Known	If stop date < study med start date, then not TEAE  If stop date >= study med start date, then TEAE
	Partial	Impute stop date as latest possible date (i.e. last day of month if day unknown or 31st December if day and month are unknown), then:  If stop date < study med start date, then not TEAE

[figure not shown]
Page 40 of 42

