If a participant dies during participation in the study or during a recognized follow-up period, the investigator will provide IQVIA with a copy of any postmortem findings including histopathology.

New or updated information will be recorded in the originally submitted documents.

The investigator will submit any updated SAE data to IQVIA within 24 hours of receipt of the information.

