#### 6.5. Baseline

Unless otherwise specified, baseline is defined as the last non-missing measurement taken prior to reference start date (including unscheduled assessments). In absence of unscheduled assessments prior to dosing, the baseline will correspond to Day -1 assessment for physical examination, clinical safety laboratory, 12-lead ECG, PD, CCI measurements; and will correspond to Day 1, Predose assessment for vital signs. In the case where the last non-missing measurement and the reference start date coincide, that measurement will be considered pre-baseline if the assessment is planned per protocol to take place prior to study medication administration. Adverse Events (AEs) and medications commencing on the reference start date will be considered post-baseline unless otherwise indicated based on available start date/time combination or collected electronic Case Report Form (eCRF) data that identifies the

Visterra Insert
Customer Name/ Logo
Protocol VIS954-101
Page 20 of 42

Statistical Analysis Plan

individual event/medication as starting prior to study medication administration.

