### 18.1. Adverse Events

Definitions of AE, unsolicited AE, and solicited AE can be found in Section 10.3 of the clinical study protocol. Unsolicited Adverse Events (AEs) will be coded using MedDRA central coding dictionary, version 26.1.

Treatment-emergent adverse events (TEAEs) are defined as AEs that first occur or worsen in severity after the study medication administration, and up to Day 71 (including the follow-up period) after the study medication administration.

Pretreatment AEs are defined as AEs occurring prior to dosing. These events will be presented in the listings only and will not be included in the tabular summary of AEs.

See Appendix 2 for handling of partial dates for AEs. In the case where it is not possible to define an AE as treatment emergent or not, the AE will be classified by the worst case, i.e., treatment emergent. Solicited AEs are predefined local injection site reactions and systemic events for which the participant is specifically questioned, and responses recorded in the eCRF data. These are collected at predefined timepoints of 1 and 4 hours post dose (Day 1), 24 hours post dose (Day 2), and on Days 3 and 29 for tenderness, pain, erythema/redness, and induration/swelling with responses based on the severity of each condition as Mild, Moderate, Severe, or Potentially Life-threatening.

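### SAP Appendix 2 has no severity test for AEs starting before the dosing date and no start-time test on Day 1, so it conflicts with SAP 18.1 and 6.5

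*SAP*

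**What the plan says.** **Definition.** SAP 18.1: "Treatment-emergent adverse events (TEAEs) are defined as AEs that first occur or worsen in severity after the study medication administration". The window runs to Day 71. The same section defines pretreatment AEs as those occurring before dosing and keeps them in listings, out of the tables. It refers to Appendix 2 for partial dates and counts an event as treatment-emergent when its status cannot be determined.

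**Algorithm.** SAP Appendix 2 has three groups of rows for AEs:
- Known start date: "If start date < study med start date, then not TEAE" and "If start date >= study med start date, then TEAE", whatever the stop date.
- "Partial, but known components show that it cannot be on or after study med start date": not a TEAE, whatever the stop date.
- "Partial, could be on or after study med start date OR Missing": the stop date decides, and a missing stop date gives a TEAE.

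No row mentions severity, worsening or clock time.

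**Day 1 rule.** Under SAP 6.5, an AE starting on the dosing date "will be considered post-baseline unless otherwise indicated based on available start date/time combination" or eCRF data showing that it began before administration.

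**Recording rules.** Protocol 8.4.1 collects AEs from consent, but has events that begin between consent and dosing recorded as medical history. Protocol 10.3.1 makes the exacerbation of a pre-existing condition an AE, without saying which onset date to enter. SAP 12 limits medical history to conditions that stop before study drug is given.

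**The concern.** The definition has two limbs and the algorithm implements only the first. An event that began before the dosing date and became more severe afterwards is a TEAE under 18.1 and not one under Appendix 2. It would then appear in listings only and drop out of every TEAE table, including those by maximum severity.

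The Day 1 rule errs the other way. An event with a recorded start time before the injection is pretreatment under 18.1 and pre-dose under 6.5, but Appendix 2 makes it a TEAE. Such events are plausible: participants are in-house from Day -1 and have vital signs and a PK sample taken before the injection on Day 1.

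TEAE incidence is the first primary endpoint listed. Two programmers working from different sections of the same SAP could report different counts from the same data.

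**Working it through.** The documents give no figure to reproduce. The check is to apply both rules to the same records.

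**Step 1. Inputs.** Rule A is the SAP 18.1 definition: a TEAE if onset is after dosing or severity worsens after dosing. Rule B is the Appendix 2 table, which uses start and stop dates only.

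**Step 2. Records compared.** There are nine patterns of start and stop date. One of them stops before dosing and so cannot worsen afterwards. The other eight are taken with and without post-dose worsening: 1 + 8 × 2 = 17 combinations.

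**Step 3. Result.** The rules agree in 11 combinations and disagree in 6:

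| Record | SAP 18.1 | Appendix 2 |
|---|---|---|
| Known start before dosing date, stops after dosing, worsens | TEAE | not TEAE |
| Known start before dosing date, ongoing, worsens | TEAE | not TEAE |
| Partial start that must precede dosing, stops after, worsens | TEAE | not TEAE |
| Known pre-dose start on Day 1, no worsening | not TEAE | TEAE |
| Partial start that could be on or after dosing but was truly before, stops after, no worsening | not TEAE | TEAE |
| Missing start that was truly before dosing, ongoing, no worsening | not TEAE | TEAE |

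**Step 4. Which disagreements are defects.** Rows 1 to 3 are the missing worsening limb. Row 4 is the Day 1 conflict, and there SAP 6.5 sides with 18.1. Rows 5 and 6 follow from the stated convention that an undecidable event counts as treatment-emergent. They are deliberate, and I do not count them against the plan.

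**Step 5. Can a record of the kind in rows 1 to 3 exist?** Protocol 8.4.1 points towards no, because a pre-dose event goes to medical history. But SAP 18.1 provides for pretreatment AE records. And under SAP 12, a condition still present at dosing, which is the only kind that can then worsen, is not medical history. Neither document says that a worsening opens a new record with a post-dose start date.

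**Step 6. Weight of one participant, assuming full cohorts.** Each cohort has 7 active and 2 placebo participants, and there are 6 cohorts.
- One dose level: 1/7 = 14.3 percentage points.
- Pooled placebo, 2 × 6 = 12: 1/12 = 8.3 points.
- All VIS954-treated, 7 × 6 = 42: 1/42 = 2.4 points.

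These apply to a preferred-term row. The overall TEAE row moves only if the participant has no other TEAE.

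**The case against.** The strongest reply is that a protocol-compliant database should hardly contain such records. Under Protocol 8.4.1 a pre-dose event is medical history. If it worsens, Protocol 10.3.1 makes the exacerbation an AE, and the natural entry has a post-dose start, which Appendix 2 classes correctly. This stands as an argument that the conflict is uncommon. It does not remove it, because the onset date to enter is nowhere stated and SAP 18.1 and 12 leave room for the problem record.

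A second reply is that Appendix 2 is titled as a partial-date convention, and 18.1 cites it only for that. That is fair, and nothing says it overrides 18.1. But its first row governs fully known dates, and its clearly-before partial row has the same gap.

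A third reply is that 6.5 already settles Day 1 and that the error runs towards counting more TEAEs. Both are true, but the two sections still instruct the programmer differently, and the extra events can fall in placebo as well as active groups.

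Two stronger readings should be resisted:
- A reader might take "New or updated information will be recorded in the originally submitted documents" in Protocol 10.3.4 to mean that a worsened event keeps its old start date. That sentence sits in follow-up text, between postmortem findings and updated SAE data. It concerns submitted reports and says nothing about AE start dates.
- A reader might infer that every AE starting before the injection is lost from the TEAE tables. Appendix 2 does not do that: pre-dose events on Day 1, and events with an uncertain or missing start that continue past dosing, are counted.

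**Conclusion.** The inconsistency is real and verifiable on the text. Appendix 2 omits the worsening limb of the TEAE definition for events whose start date is known to be, or must be, before the dosing date. It also disregards start time on the dosing date. The first gap can lose TEAEs and the second can add them.

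The practical effect is probably small, and the number of affected events cannot be derived. The 14-point and 8-point figures are the weight of one participant, not an estimate of bias.

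The conclusion rests on two assumptions: that some AE records carry a pre-dose start, as SAP 18.1 anticipates, and that no unpublished eCRF instruction already requires a new record at worsening. A reader might also infer that dose-escalation decisions are affected. The documents do not support that: the stopping criteria in Protocol 7.1 use seriousness and grade rather than TEAE status, and SAP 4.1 places SMC reporting outside the SAP.

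The texts should be aligned because this is a primary endpoint and the correction is trivial.

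**What to change.** Amend SAP Appendix 2 in two places.

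(a) In the row for a known start before the dosing date and the row for a partial start that must precede it, class the event as a TEAE if its severity increased after dosing. Alternatively, state that a post-dose worsening is entered as a new AE record dated at the worsening. The choice depends on whether the eCRF captures changes in severity within a record, which the documents do not say. The alternative works only if sites actually follow that convention.

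(b) When the start date equals the dosing date, apply the SAP 6.5 rule: use the start time or the eCRF pre-dose indicator, and default to TEAE only when neither is available.

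The cost is about two lines of SAP text and the matching program code. Under the alternative in (a), a line in the eCRF completion instructions is also needed if none exists. No design change follows.
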